Single 12-lead ECG (supine)	X															X	Single screening ECG but may be obtained at additional times, when deemed clinically necessary.	

Procedure	Screening	Study Day																Comments
		-1	1	3	5 ±1d	8 ±1d	11 ±1d	15 ±2d	22 ±2d	29 ±2d	36 ±2d	43 ±2d	50 ±2d	57 ±3d	64 ±2d	71 ±3d	85 ±3d or ED	
Mirikizumab administration (2 injections per dose)	-28 to -2 days prior to Day 1			X														See Section 7.1. Subjects will fast (only water is allowed) from 1 hour before until 1 hour after dosing. Injections at Times 0 and 20 ± 2 min.
CCI				1														Assess within the first minute and then, if there is bleeding, at 1-min intervals following the injection until the bleeding stops. See Section 9.4.5.2.
CCI				1, 5, 15, 30, 60, 120, 240													Assess all injections as described in Section 9.4.5.3. Time points on Day 1 after each injection are 
 
• within 1 min,
 
• 5 min (±1.5 min)
 
• 15 and 30 min (each ±2 min), and
 
• 60, 120, and 240 min (each ±5 min).
 
• For VAS, see Section 9.4.5.3.1.
 
	
Mirikizumab PK sample			P	X	X	X	X	X	X	X	X	X	X	X	X	X		

Procedure	Screening -28 to -2 days prior to Day 1	Study Day																Comments
		-1	1	3	5 ±1d	8 ±1d	11 ±1d	15 ±2d	22 ±2d	29 ±2d	36 ±2d	43 ±2d	50 ±2d	57 ±3d	64 ±2d	71 ±3d	85 ±3d or ED	
CC1 F			P					X		X							X	
CC1 F		X																
AE and concomitant medication		X	X	X	X	X	X	X	X	X	X	X	X	X	X	X	ISRs will be reported on supplemental ISR form, and not as AEs	

Abbreviations: AE = adverse event; BMI = body mass index; CRU = clinical research unit; d = day; ECG = electrocardiogram; ED = early discontinuation;

FSH = follicle-stimulating hormone; ISR = injection-site reaction; min = minutes; P = pre-dose; PK = pharmacokinetic(s); SC = subcutaneous; TB = tuberculosis; VAS = visual analog scale.

a Administration of the pain VAS is mandatory at 1, 5, and 15 min regardless of whether pain is reported as "yes" or "no" during the injection-site assessment. At other time points, the VAS is administered only if pain is reported as "yes" during an injection-site assessment.

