### 9.2. Adverse Events

Investigators are responsible for monitoring the safety of subjects who have entered this study and for alerting Lilly or its designee to any event that seems unusual, even if this event may be considered an unanticipated benefit to the subject.

The investigator is responsible for the appropriate medical care of subjects during the study.

Investigators must document their review of each laboratory safety report.

The investigator remains responsible for following, through an appropriate health care option, AEs that are serious or otherwise medically important, considered related to the IP or the study, or that caused the subject to discontinue the IP before completing the study. The subject should be followed up until the event resolves, stabilizes with appropriate diagnostic evaluation, or is reasonably explained. The frequency of follow-up evaluations of the AE is left to the discretion of the investigator.

The investigator will record all relevant AE and SAE information in the eCRF. After the informed consent form is signed, site staff will record, via eCRF, the occurrence and nature of each subject's preexisting conditions. Additionally, site staff will record any change in the condition(s) and the occurrence and nature of any AEs.

The investigator will interpret and document whether or not an AE has a reasonable possibility of being related to study treatment, study device, or a study procedure, taking into account the disease, concomitant treatment, or pathologies.

A "reasonable possibility" means that there is a potential cause and effect relationship between the IP, study device and/or study procedure, and the AE.

Planned surgeries should not be reported as AEs, unless the underlying medical condition has worsened during the course of the study.

Prospective collection of ISRs at predefined time points is included as part of this protocol. As such, any identified ISRs will not be collected as AEs but will instead be recorded using the predefined ISR collection tools.

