### **9.2.1. Serious Adverse Events**

An SAE is any AE from this study that results in 1 of the following:

- death
- initial or prolonged inpatient hospitalization
- a life-threatening experience (ie, immediate risk of dying)
- persistent or significant disability/incapacity
- congenital anomaly/birth defect
- important medical events that may not be immediately life threatening or result in death or hospitalization but may jeopardize the subject or may require intervention to prevent 1 of the other outcomes listed in the definition above

Site staff must alert the Lilly CRP/CP, or its designee, of any SAE as soon as practically possible.

Additionally, site staff must alert Lilly Global Patient Safety, or its designee, of any SAE within 24 hours of investigator awareness of the event via a sponsor-approved method. If alerts are issued via telephone, they are to be immediately followed up with official notification on study-specific SAE forms. This 24-hour notification requirement refers to the initial SAE information and all follow-up SAE information.

Although all AEs are recorded in the eCRF after signing informed consent, SAE reporting to the sponsor begins after the subject has signed informed consent and has received IP. However, if an SAE occurs after signing informed consent, but prior to receiving IP, AND is considered Reasonably Possibly Related to a study procedure then it MUST be reported.

Investigators are not obligated to actively seek AEs or SAEs in subjects once they have discontinued from and/or completed the study (the subject summary eCRF has been completed). However, if the investigator learns of any SAE, including a death, at any time after a subject has been discharged from the study, and he/she considers the event reasonably possibly related to the study treatment or study participation, the investigator must promptly notify Lilly.

Pregnancy (maternal or paternal exposure to IP) does not meet the definition of an AE. However, to fulfill regulatory requirements any pregnancy should be reported following the SAE process to collect data on the outcome for both mother and fetus.

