#### **9.2.1.1. Adverse Device Effects**

Any AE believed to have a reasonable possibility of being related to or associated with an issue with the PFS, such as a malfunction or a deficiency, is considered an adverse device event.

These events must be clearly indicated as such in the eCRF and reported to the sponsor. A product complaint should also be reported.

For the purposes of this protocol, “unanticipated” serious adverse device effect means any SAE alleged to have a reasonable possibility of being associated with or related to the device, which was not previously defined as anticipated in study documents, such as the device IB or Instructions for Use. The SAE relatedness must be clearly indicated as such in the eCRF, and reported to the sponsor within 24 hours of site knowledge of the event. A product complaint should also be reported.

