**Appendix 1. Abbreviations and Definitions**

---

Term	Definition
ADA	antidrug antibody
AE	adverse event: Any untoward medical occurrence in a patient or clinical investigation subject administered a pharmaceutical product that does not necessarily have a causal relationship with this treatment. An AE can therefore be any unfavorable and unintended sign (including an abnormal laboratory finding), symptom, or disease temporally associated with the use of a medicinal (investigational) product, whether or not related to the medicinal (investigational) product.
ALP	alkaline phosphatase
ALT	alanine aminotransferase
AUC	area under the concentration versus time curve
AUC(0-∞)	area under the concentration versus time curve from time zero to infinity
AUC(0-tlast)	area under the concentration versus time curve from time zero to time t, where t is last the time point with a measurable concentration
blinding	A procedure in which 1 or more parties to the study are kept unaware of the treatment assignments. Unless otherwise specified, blinding will remain in effect until final database lock.  A single-blind study is one in which the investigator and/or site staff are aware of the treatment, but the subject is not, or vice versa; or when the sponsor is aware of the treatment, but the investigator, site staff, and the subject are not. A double-blind study is one in which neither the subject nor any of the investigator or sponsor staff who are involved in the treatment or clinical evaluation of the subjects are aware of the treatment received.
BMI	body mass index
CI	confidence interval
Cmax	maximum observed drug concentration
complaint	A complaint is any written, electronic, or oral communication that alleges deficiencies related to the identity, quality, purity, durability, reliability, safety or effectiveness, or performance of a drug or drug delivery system.
compliance	Adherence to all the study-related requirements, good clinical practice (GCP) requirements, and the applicable regulatory requirements.

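### The rule keeping injection-site reactions out of AE reporting is not limited to non-serious reactions, so it conflicts with the SAE definition and its 24-hour alert

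*Protocol*

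**What the plan says.** **The exclusion.** Protocol Section 9.2 says that "any identified ISRs will not be collected as AEs but will instead be recorded using the predefined ISR collection tools". The comment on the AE row of the Schedule of Activities says that "ISRs will be reported on supplemental ISR form, and not as AEs". Neither sentence mentions seriousness, cause or relation to the syringe.

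**The pathways that depend on AE status.** Section 9.2.1 begins its definition with "An SAE is any AE from this study that results in 1 of the following" and requires that "site staff must alert Lilly Global Patient Safety, or its designee, of any SAE within 24 hours of investigator awareness of the event". Section 9.2.1.1 defines an adverse device event as "Any AE believed to have a reasonable possibility of being related to or associated with an issue with the PFS", and an unanticipated serious adverse device effect as a kind of SAE. SAP Section 9.4.1 defines a TEAE as a kind of AE, builds the TEAE tables from those events and lists the SAEs.

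**The general definition.** Appendix 1 of the protocol opens its definition of an AE with "Any untoward medical occurrence in a patient or clinical investigation subject administered a pharmaceutical product". An ISR falls within it.

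**The concern.** Keeping ordinary ISRs on a dedicated form is a reasonable design choice and is not questioned here. The difficulty is the reach of the exclusion. It covers every ISR, while the expedited alert, the device-event flag and the safety outputs are all worded for events that are AEs. A serious ISR is then subject to two instructions that disagree.

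At stake is the handling of a rare but important event. The test formulation has not been given to people before, and it was developed to reduce ISRs. The visible secondary endpoint consists of TEAEs and SAEs. A serious ISR held only on the ISR form would not count towards that endpoint, and the visible text would attach no 24-hour alert to it.

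**Working it through.** No rate or formula applies to the conflict itself, so the check sets the texts side by side.

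1. **Is the exclusion qualified?** No, in neither place. The sentence just before it in Section 9.2 shows that the drafters did write exceptions: "Planned surgeries should not be reported as AEs, unless the underlying medical condition has worsened during the course of the study". The ISR sentence has no such clause.

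2. **What happens to a serious ISR under each text?**

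| Text followed | Form | 24-hour alert | SAP 9.4.1 TEAE tables and SAE listing |
|---|---|---|---|
| Schedule comment, read literally | ISR form only | Not triggered | Absent |
| Appendix 1 with Section 9.2.1 | Reported as an SAE | Triggered | Present |
| Section 9.2, read as a rule about forms only | ISR form | Triggered, since the event is still an AE | Unclear, since the event was not collected as an AE |

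3. **Which serious ISRs do other visible rules already cover?**
   - Acute allergic or hypersensitivity reactions must be recorded as AEs (Section 7.4.1) and are AEs of special interest (Section 9.2.1.2).
   - Infection is also an AE of special interest (Section 9.2.1.2).
   - Section 9.2 makes investigators responsible for "alerting Lilly or its designee to any event that seems unusual". That duty has no 24-hour limit and does not place the event in the AE data.

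   What remains is a serious local reaction that is neither allergic nor infectious.

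4. **What is left of the syringe-fault case?** Section 9.2.2 already sends a product complaint form to the sponsor within 24 hours, so the sponsor learns of the fault. What may be missing is the adverse device event flag in the eCRF, because Section 9.2.1.1 attaches it to AEs.

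5. **When does the rule apply?** The visible injection-site time points end at 240 minutes on Day 1, while AEs are collected to Day 85 and the exclusion is not confined to Day 1. An ISR that becomes serious after discharge is therefore subject to the same conflict. The label of the assessment row is redacted, so this holds for the visible schedule only.

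6. **How many injections does the rule cover?** Each subject receives 2. For completers, 48 × 2 = 96; at the enrolment cap, 60 × 2 = 120. The documents give no rate of serious ISRs, so no probability of an event can be calculated.

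**The case against.** The strongest reply is that Section 9.2 is only a rule about data capture. It says how ISRs are collected and never says that an ISR is not an AE. Section 9.2.1 defines an SAE by the event and its outcome, whichever form is used, and Appendix 1 is unchanged. Pregnancy supports this reply: Section 9.2.1 expressly takes it outside the AE definition and so has to route it through the SAE process. Nothing comparable is said of ISRs. On this reading a serious ISR is still an SAE and the alert still applies.

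Much of this stands. A reader might infer that the protocol takes serious ISRs out of SAE reporting, or tells staff to withhold them. The documents do not support that inference; they show an internal conflict. A reader might also infer that a syringe-fault ISR never reaches the sponsor. The complaint route in Section 9.2.2 shows otherwise.

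Three further points reduce the concern:
- ISR data would not vanish. SAP Section 9.1 lists all data held in the database, and under Protocol Section 9.4.6 the sponsor's clinical staff monitor safety data throughout.
- Protocol Section 3.2.1 reports no SAEs in the Phase 1 studies, although Section 3.2.2 places ISRs among the most frequent TEAEs there.
- Protocol Section 9.4.5.3 and the text of SAP Sections 9.4.9 and 9.4.10 are redacted and may hold a rule for serious ISRs.

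The reply does not dispose of the Schedule comment. That comment concerns how ISRs are reported, and it directly contradicts Section 9.2.1 for a serious ISR. Sections 9.2, 9.2.1 and 9.2.1.1 and the Schedule comment are legible, and none points to an exception elsewhere. Routing of a serious event should not depend on which of two sentences staff happen to follow.

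**Conclusion.** The point holds as an internal conflict of low magnitude that is cheap to remove. On the visible text, staff who follow the Schedule could leave a serious, non-allergic, non-infectious ISR on the ISR form alone, outside the 24-hour alert and the SAP Section 9.4.1 outputs. Staff who follow Section 9.2.1 would report it. The syringe-fault part is minor and comes down to one eCRF flag.

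The low rating rests on earlier ISRs being mostly pain of mild to moderate degree and limited erythema (Protocol Section 3.2), and on the other routes that cover allergic, infectious and unusual events. Confidence is moderate, because absence of an exception can be asserted only for the legible text. The primary pharmacokinetic analysis is not affected.

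**What to change.** In Protocol Section 9.2 and the Schedule comment, limit the exclusion to non-serious ISRs and add a sentence such as:

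> An ISR that meets a seriousness criterion in Section 9.2.1 is entered on the ISR form, and is also recorded as an AE and reported as an SAE. An ISR thought to result from a PFS malfunction or deficiency is likewise also recorded as an AE and flagged under Section 9.2.1.1.

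All other ISRs stay on the ISR form only. In SAP Section 9.4.1, state that ISRs recorded as AEs under this rule enter the TEAE tables and, if serious, the SAE listing. If redacted Protocol Section 9.4.5.3 already contains the exception, a cross-reference from Section 9.2 and the Schedule comment is enough.

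The cost is a sentence or two in the protocol, repeated in the Schedule comment, and one sentence in the SAP. No new visit, procedure or form is needed. The downside is that a rare serious or syringe-related ISR is entered twice, and the ISR form and AE record must be reconciled.

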### **9.2.1. Serious Adverse Events**

An SAE is any AE from this study that results in 1 of the following:

- death
- initial or prolonged inpatient hospitalization
- a life-threatening experience (ie, immediate risk of dying)
- persistent or significant disability/incapacity
- congenital anomaly/birth defect
- important medical events that may not be immediately life threatening or result in death or hospitalization but may jeopardize the subject or may require intervention to prevent 1 of the other outcomes listed in the definition above

Site staff must alert the Lilly CRP/CP, or its designee, of any SAE as soon as practically possible.

Additionally, site staff must alert Lilly Global Patient Safety, or its designee, of any SAE within 24 hours of investigator awareness of the event via a sponsor-approved method. If alerts are issued via telephone, they are to be immediately followed up with official notification on study-specific SAE forms. This 24-hour notification requirement refers to the initial SAE information and all follow-up SAE information.

Although all AEs are recorded in the eCRF after signing informed consent, SAE reporting to the sponsor begins after the subject has signed informed consent and has received IP. However, if an SAE occurs after signing informed consent, but prior to receiving IP, AND is considered Reasonably Possibly Related to a study procedure then it MUST be reported.

Investigators are not obligated to actively seek AEs or SAEs in subjects once they have discontinued from and/or completed the study (the subject summary eCRF has been completed). However, if the investigator learns of any SAE, including a death, at any time after a subject has been discharged from the study, and he/she considers the event reasonably possibly related to the study treatment or study participation, the investigator must promptly notify Lilly.

Pregnancy (maternal or paternal exposure to IP) does not meet the definition of an AE. However, to fulfill regulatory requirements any pregnancy should be reported following the SAE process to collect data on the outcome for both mother and fetus.

#### **9.2.1.1. Adverse Device Effects**

Any AE believed to have a reasonable possibility of being related to or associated with an issue with the PFS, such as a malfunction or a deficiency, is considered an adverse device event.

These events must be clearly indicated as such in the eCRF and reported to the sponsor. A product complaint should also be reported.

For the purposes of this protocol, “unanticipated” serious adverse device effect means any SAE alleged to have a reasonable possibility of being associated with or related to the device, which was not previously defined as anticipated in study documents, such as the device IB or Instructions for Use. The SAE relatedness must be clearly indicated as such in the eCRF, and reported to the sponsor within 24 hours of site knowledge of the event. A product complaint should also be reported.

#### **9.2.1.2. Adverse Events of Special Interest**

The following AEs of special interest will be used to determine the safety and tolerability of mirikizumab formulations administered through PFS in this clinical study.

Adverse events of special interest for mirikizumab are

- Infection
- systemic allergic/hypersensitivity reactions

If infections or allergic/hypersensitivity reactions are reported, site staff will provide details on these events as instructed on the eCRF. A PK, immunogenicity, and hypersensitivity cytokine panel ([Appendix 6](#)) will be collected when possible for any subject who experiences an AE of systemic allergic/hypersensitivity reaction during the study.

#### **9.2.1.3. Suspected Unexpected Serious Adverse Reactions**

Suspected unexpected serious adverse reactions (SUSARs) are serious events that are not listed in the IB and that the investigator reports as related to IP or procedure. Lilly has procedures that will be followed for the recording and expedited reporting of SUSARs that are consistent with global regulations and the associated detailed guidances.

### **9.2.2. Complaint Handling**

Lilly collects product complaints on IPs and drug delivery systems used in clinical trials to ensure the safety of study subjects, monitor quality, and to facilitate process and product improvements.

Subjects should be instructed to contact the investigator as soon as possible if they have a complaint or problem with the IP or drug delivery system so that the situation can be assessed.

The investigator or designee is responsible for handling the following aspects of the product complaint process in accordance with the instructions provided for this study:

- recording a complete description of the product complaint reported and any associated AEs using the study-specific complaint forms provided for this purpose
- faxing the completed Product Complaint Form within 24 hours to Lilly or its designee

If the investigator is asked to return the product for investigation, he or she will return a copy of the product complaint form with the product.

### **9.3. Treatment of Overdose**

For the purposes of this study, an overdose of mirikizumab is considered any dose higher than the 200-mg dose assigned through randomization. Syringes used in this study can deliver a 1-mL volume of mirikizumab and each dose will require 2 syringes.

There is no specific antidote for mirikizumab. In the event of an overdose, the subject should receive appropriate supportive care and any AEs should be documented.

Refer to the mirikizumab IB for further details.

### **9.4. Safety**

#### **9.4.1. *Laboratory Tests***

For each subject, laboratory tests detailed in [Appendix 2](#) should be conducted according to the Schedule of Activities (Section [2](#)).

#### **9.4.2. *Vital Signs***

For each subject, vital sign measurements should be conducted according to the Schedule of Activities (Section [2](#)). Additional vital signs may be measured during the study, if warranted.

Blood pressure and pulse rate should be measured after the subject has been sitting for at least 5 minutes.

If the subject feels unable to stand, supine vital signs only will be recorded.

Unscheduled orthostatic vital signs should be assessed, if possible, during any AE of dizziness or posture-induced symptoms.

#### **9.4.3. *Electrocardiograms***

For each subject, a single 12-lead ECG should be collected according to the Schedule of Activities (Section [2](#)).

Electrocardiograms must be recorded before collecting any blood samples. Subjects must be supine for approximately 5 to 10 minutes before ECG collection and remain supine but awake during ECG collection. Electrocardiograms may be obtained at additional times, when deemed clinically necessary. All ECGs recorded should be stored at the study site.

Electrocardiograms will be interpreted by a qualified investigator (the physician or qualified designee) at the site as soon after the time of ECG collection as possible, and ideally while the subject is still present, to determine whether the subject meets entry criteria at the relevant visit(s) and for immediate subject management, should any clinically relevant findings be identified.

